[name], a Health Care Economist at Brandeis University, will lead the economic evaluation of the program. We will collect data on the costs associated with program implementation from the clinical site and from participants at each follow-up interview (including travel costs). Operating costs under each arm will be collected through a customized cost assessment tool that [name] developed using some of our own programmatic data for cardiac rehabilitation and lifestyle modification¹²² and counseling services.^{148,165} To assess costs to participants (e.g. travel expenses, time spent, and out-of-pocket expenses), we will use a tool created for our prior study that adapted the Client Drug Abuse Treatment Cost Analysis Program (DATCAP; www.datcap.com/client.htm) for use in cardiac rehabilitation. Direct nonmedical and indirect costs include the value of time of participants attending the program, waiting, traveling, or exercising, as well as transportation expenses.

Quality-adjusted life years (QALYs)¹⁵⁰ for each condition will be calculated using the health-related quality of life (HRQL) measure.¹³³ The ratio of cost per QALY will be modeled incorporating meta-analysis data from randomized-controlled trials of CR after a coronary event^{18,166} to estimate the cost-effectiveness of incentives encouraging CR compared to standard CR. This cost-effectiveness model will also include hospitalization costs averted and possible increases in ambulatory costs if CR use, associated testing, and ambulatory services increase for those in treatment conditions.³³ Similar to another recent cost-effectiveness study of CR, we will perform the analysis with two contrasting time perspectives – the period of follow-up alone and a lifetime perspective – based on a carefully calibrated model of project utilization and costs.¹⁴ The former provides a more conservative, short-term analysis closely tied to the observed data. The latter provides a long-run perspective.

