The proposed project is a four parallel-condition, randomized controlled trial to assess the efficacy of the use of incentives and case management for increasing CR participation in a lower-SES cardiac population. The study population will be comprised of 209 lower-SES patients with a recent CR-qualifying coronary event (including congestive heart failure). The experimental conditions will be: 1) an intervention where patients are assigned a case manager (CM) to coordinate their care 2), an intervention wherein patients earn financial incentives (FI) contingent on participating in CR, or 3) a combination of these two interventions (FI+CM). These intervention conditions will be compared to a usual care control (i.e., referral to CR). The main outcome measure for this project will be CR participation and adherence (% who complete 30+ sessions, # of sessions completed). Secondary outcomes will include improvements in executive function, fitness (PVO2), and quality of life over four months and at one-year follow-up, as well as rehospitalizations and emergency department visits through one-year follow-up. A comprehensive cost effectiveness analysis of the interventions will be conducted, incorporating rehospitalization rates and the cost of both delivering and receiving the treatment.

Procedures: *Describe all procedures (sequentially) to which human participants will be subjected. Identify all procedures that are considered experimental and/or procedures performed exclusively for research purposes. Describe the types, frequency and duration of tests, study visits, interviews, questionnaires, etc. Include required screening procedures performed before enrollment and while on study. Please provide in table, list or outline format for ease of review. (describe and attach all instruments)*

Note: *A clinical research protocol may involve interventions that are strictly experimental or it may involve some aspect of research (e.g., randomization among standard treatments for collection and analysis of routine clinical data for research purposes). It is important for this section to distinguish between interventions that are experimental and/or carried out for research purposes versus those procedures that are considered standard therapy. In addition, routine procedures performed solely for research purposes (e.g., additional diagnostic/follow-up tests) should be identified.*

All procedures are being undertaken for research purposes.

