Study Measures: Study measures are taken by clinical staff blinded to treatment condition at three timepoints: baseline, end of treatment (four months) and one-year follow-up.

Demographic Information: We will collect the following sociodemographic data: age, gender, educational attainment, race/ethnicity, smoking status, marital status, and health insurance status at baseline. These demographic measures will allow us to characterize the population.

CO level: Carbon Monoxide level (CO) will be collected using a coVita carbon monoxide measuring device. The participant will be required to breathe slowly through a cardboard tube to obtain this measurement. This measurement will quantify recent exposure to carbon monoxide (e.g. smoke/secondhand smoke/car exhaust/heater emissions).

Maximal Exercise Capacity: Maximal exercise capacity will be assessed on a treadmill using measurements of peak oxygen uptake, duration of treadmill exercise and maximal exercise intensity in METS. A continuous modified-Balke protocol will be used, with exercise increasing gradually at 1 MET increments at 2-minute intervals. Exercise is EKG monitored and stopped prior to exhaustion if the patient develops progressive angina, > 2mm ST segment depression, exercise induced hypertension (230 systolic, 105 diastolic), severe arrhythmias, dizziness or symptomatic hypotension. The occurrence of any concerning responses, other than high threshold angina, excludes a patient from the training protocol unless effective therapy is instituted. Patients will perform the maximal stress test taking their usual medications at a standardized time of day. The clinical staff at UVMMC have extensive experience

measuring peak exercise capacity in patients in the CR setting.¹²⁷ In lieu of a maximal stress test at CR exit, estimated METS while exercising on the treadmill may be used at the final CR session as a clinical measure of fitness at exit.

Socio-Cognitive Measures: We will assess current depressive symptoms (Beck Depression Inventory, BDI, Patient Health Questionnaire (PHQ-2)^{128,129} as well self-reported adaptive functioning and problems (ASEBA - Achenbach System of Empirically Based Assessment.¹³⁰ We will also assess self-reported social support (ISEL - Interpersonal support evaluation list).¹⁴⁷

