By definition, primary outcome data will not be missing since it focuses on program participation. For other variables, minor amounts of missing data, due to factors other than dropout from the CR program, will be ignored, leading to deletion of cases in regression analyses. However, if substantial amounts of missing data of key predictor variables exist, we will explore the randomness of missing data using Little's MCAR (missing completely at random) test in SPSS 24. If we cannot reject the null hypothesis, we will proceed to use multiple imputation procedures in SAS 9.4 (PROC MI and PROC MIANALYZE) to generate results based on imputed data.

Although this study is powered for our primary outcome of adherence to CR, we will also carefully examine improvements in fitness, and other health outcomes (quality of life, maximal exercise capacity, weight, waist measurements) between conditions, using the pre-planned comparisons outlined for the primary outcome. Additionally, we will examine changes in executive function measures and socio-cognitive status at 4 and 12 months. Changes in these scores will also be examined for possible gender interactions. Since multiple observations for each participant will be obtained, the general analytic approach will consist of analysis of covariance (ANCOVA) at 4 months and repeated measures analysis of variance (ANOVA) at 12 months. Formal testing will examine the condition by time interaction term to assess differential time changes between treatment conditions. Post-hoc comparisons between conditions will be made if significant interactions are observed.

Survival analyses will be conducted once all participants have completed the 36 sessions of their CR program (or, alternatively, have dropped out of the program). Preliminary analyses of all other outcome measures will occur upon collection of all 4-month measures across all participants. Final analyses of secondary outcome measures, using repeated measures procedures, will be conducted upon collection of all 12- month measures across all participants. Across all tests, statistical significance will be defined as $p < 0.05$ (2-tailed).

Cost Effectiveness Analyses

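### Treadmill METs estimated at the last CR session may replace the exit stress test, and no SAP rule keeps them out of the between-arm fitness comparison

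*Combined protocol and SAP*

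**What the plan says.** The Study Design section of the protocol lists as secondary outcomes, with a one-year assessment as well, "improvements in executive function, fitness (PVO2), and quality of life over four months". Study Measures schedules assessments "at three timepoints: baseline, end of treatment (four months) and one-year follow-up". Under Maximal Exercise Capacity the reference method is a graded test: "Maximal exercise capacity will be assessed on a treadmill using measurements of peak oxygen uptake, duration of treadmill exercise and maximal exercise intensity in METS". The same paragraph ends with a permission: "In lieu of a maximal stress test at CR exit, estimated METS while exercising on the treadmill may be used". The rest of that sentence ties the value to the last CR session and describes it as a clinical fitness measure.

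The SAP (Primary and Secondary Data Analyses), repeating the protocol's Data Analysis text, says: "we will also carefully examine improvements in fitness, and other health outcomes (quality of life, maximal exercise capacity, weight, waist measurements) between conditions". The pairwise comparisons are those planned for the primary outcome. The models are ANCOVA at 4 months and repeated measures ANOVA at 12 months.

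Four things are not stated anywhere: who receives which exit measure, how the two would be put on one scale, whether the model accounts for test type, and what becomes of peak VO2 when no maximal test is done.

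**The concern.** Estimated METs during a training session are not measured oxygen uptake, and the plan does not say they represent a maximum. They can be recorded only for someone who attends CR. Usual-care participants come in for study assessments whether or not they attend CR, so a maximal test at the study visit does not depend on attendance, whereas the substitute does. Attendance is what the interventions are meant to change.

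If the substitute enters the fitness variable, part of any between-arm difference could reflect which measure was used. If it does not, exit peak VO2 may be absent for the attenders who were not tested, and so more often in arms with better attendance. Either way the comparison loses some of the protection of randomisation. Fitness is one of the named outcomes for the first secondary objective, which asks whether differences in attendance affect health.

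**Working it through.** **1. The plan's attendance figures.** The protocol's Power paragraph gives 54% (incentives) and 28% (usual care) completing 30 or more sessions in the prior trial; the SAP attaches the same percentages to 36 sessions. To confirm that these figures drive the plan, reproduce the sample size (two-sided 0.05, 80% power), with mean proportion 0.41:

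n = [1.96 × √(2 × 0.41 × 0.59) + 0.8416 × √(0.54 × 0.46 + 0.28 × 0.72)]² / 0.26² = (1.363 + 0.565)² / 0.0676 ≈ 55 per arm.

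The likelihood-ratio test that the plan names gives 79.7% power at 55, 80.4% at 56 and 81.1% at 57. The stated 57 (protocol) and 56 (SAP) are therefore reproduced. The plan gives no power figure for fitness.

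**2. Share of substituted values.** Let q be the share of completers given the substitute (assumed equal in both arms), with completion as a proxy for having an exit session. The shares are 0.54q and 0.28q. Their ratio is 54/28 = 1.93 for any q above zero, and their difference is 0.26q.

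**3. Artefact if the values are pooled.** Let D be the mean of session METs minus maximal-test METs (assumed equal in both arms). Each arm mean shifts by its share times D, so the arm difference shifts by q × 0.26 × D. Adjusting for baseline does not remove this, because the shift arises at exit.

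| q | Substituted: incentives vs usual care | \|D\| = 0.5 | \|D\| = 1 | \|D\| = 2 |
|---|---|---|---|---|
| 0 | 0% vs 0% | 0 | 0 | 0 |
| 0.25 | 13.5% vs 7% | 0.03 | 0.065 | 0.13 |
| 0.5 | 27% vs 14% | 0.065 | 0.13 | 0.26 |
| 1 | 54% vs 28% | 0.13 | 0.26 | 0.52 |

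(Entries are the absolute artefact in METs.)

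**4. Sign.** Suppose session METs are a fraction f of a true peak of 6 METs (assumption), so D = (f − 1) × 6. At q = 1, f = 0.9 gives 0.26 × (−0.6) = −0.16 METs, f = 1 gives zero, and f = 1.1 gives +0.16 METs.

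**5. Effect on the test.** Assume no true fitness difference, a residual SD of 1.5 to 2.0 METs, and all 57 and 38 participants analysed. The standard error is SD × √(1/57 + 1/38) = SD × 0.209, or 0.31 to 0.42 METs. The two-sided rejection rate, nominally 5%, becomes:
- 5% to 7% when q × |D| is 0.5 MET or less;
- 9.5% to 13% at q × |D| = 1;
- 24% to 38% at q × |D| = 2.

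**6. If only measured peak VO2 is analysed.** The shares in step 2 become missing values. At q = 1 that is 0.54 × 57 = 30.8 of 57 and 0.28 × 38 = 10.6 of 38, leaving about 26 and 27 participants, none of them completers. The SAP would delete cases for minor missingness. It offers multiple imputation only for substantial missingness in key predictor variables, and only when Little's test does not reject MCAR. Fitness is an outcome, and this missingness would follow attendance and arm.

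**The case against.** The permission is optional, and no passage says the estimates will be analysed as peak VO2. The sentence calls the value a clinical measure, and the Study Design section names the outcome as peak VO2. A reader might infer that the comparison definitely mixes two measures. The documents do not support that: they establish that the exit test may be replaced, not that the replacement enters the same variable. This stands, and it is why the point is worded as a possibility. It does not dispose of the concern, because the alternative is the selective missingness in step 6.

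CR exit and the 4-month study visit may also be separate events. If the 4-month maximal test is done whatever happens at exit, a clean comparison is available. The documents leave this open, and the fix relies on that visit.

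A reader might further infer that a successful arm would appear to gain less fitness. That holds only if D is negative; the sign reverses if session estimates exceed the measured peak. Nor do the documents support any particular MET figure: they give neither q nor D, and the larger entries assume that every completer is substituted. The completion rates are a proxy from a prior trial and cover only incentives versus usual care, not the other planned comparisons.

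Finally, fitness is a secondary outcome for which the study is not powered, and the permission extends only to CR exit, not to the one-year test. Both are correct and limit the weight of the point.

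**Conclusion.** The gap is real. As written, the plan allows a training-session estimate to stand in for the exit maximal test, and nothing in the SAP keeps it out of the 4-month comparison, or out of the repeated measures analysis if that uses the 4-month value. The dependence on arm is inferred from the design: it follows if the option is used at similar rates among attenders and attendance differs as planned.

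Direction and size are unknown. The artefact is q × 0.26 × D METs, so rare use or a small gap makes it negligible, while full use with a 1-MET gap gives 0.26 METs. If only measured values are used, the problem becomes missing data that could concentrate in the better-attending arms. The primary adherence outcome is untouched. The point merits a change because it affects a named secondary outcome and costs little to close.

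**What to change.** In the protocol and SAP:

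- State that session-estimated METs are never entered as peak VO2 or maximal exercise capacity.
- Base the 4-month between-arm fitness comparison on the maximal test at the scheduled 4-month assessment, and say how that visit relates to CR exit.
- Report session METs separately and descriptively.
- Tabulate test type and missing tests by arm.
- Extend multiple imputation explicitly to this outcome under a missing-at-random assumption, with arm, baseline fitness, sessions attended and session METs in the imputation model. Drop the MCAR test as a condition: it would withhold imputation when missingness is visibly related to other data, which is when imputation is most needed.

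The cost is wording and some extra analysis. The downside is more missing exit peak VO2 values, possibly concentrated in better-attending arms. Imputation helps only if some attenders have a measured test: with q near 1 there would be almost no completers from whom to learn the relation, so the table of missing tests should accompany the result. The change concerns the research outcome only and leaves clinical practice at CR exit as it is.

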If the CR clinics (UVMMC, Copley Hospital, Northwestern Medical Center) cease in-person visits, session completion will be calculated by tracking remote participation. Study participants across arms will be expected to complete two CR sessions per week. One session will consist of completing the weekly telemedicine call conducted by CR staff and one session will consist of completing a recommended step goal for that day, as confirmed by an Omron pedometer. A session will be coded as missed (excused or unexcused, depending on the situation) if a participant fails to send a step count or fails to complete the telemedicine call from the CR case manager.

For research involving survey, questionnaires, etc.: Describe the setting and the mode of administering the instrument and the provisions for maintaining privacy and confidentiality. Include the duration, intervals of administration, and overall length of participation. (describe and attach all instruments)

Not applicable

Questionnaires will be administered at intake, after 4 months, and at one year. All questionnaires will be administered in a private setting at the Cardiac Rehabilitation Facility. Questionnaires should take approximately one hour to complete.

As listed above the following questionnaires will be administered (and are attached):

Beck Depression Inventory. Note: the BDI includes a question about suicidal thoughts. If a subject endorses this item research staff will follow the attached suicidality protocol.

MacNew Cardiac Health Status Questionnaire

TCAP

Interpersonal Support Evaluation List

International Physical Activity Questionnaire (IPAQ, brief form)

Executive Function Battery Questionnaires:

The Time Perspective Questionnaire – Exercise (TPQ)

Euroqol (Quality of Life)

Achenbach System of Empirically Based Assessments (ASEBA) – Adult Self Report or Older Adult Self Report

Behavior Rating Inventory of Executive Function (BRIEF)

Data Collection: Questionnaire Administration Amidst Contact Restrictions (e.g. COVID-19)

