Whenever possible, paper questionnaires will be completed remotely, either by mail (completed and returned by the study participant) or with the researcher over the phone. If in-person research visits are not allowed the following assessments will not be collected: IQ test (WASI), Stop Signal Task (SST), Delay Discounting Task (DD), Trail Making Task (TMT), Digit Span Task. If in-person research visits are allowable these assessments will be completed using appropriate distancing measures and PPE as is outlined in our approved lab safety reopening plan (attached).

Statistical Considerations: *Delineate the precise outcomes to be measured and analyzed. Describe how these results will be measured and statistically analyzed. Delineate methods used to estimate the required number of subjects. Describe power calculations if the study involves comparisons. Perform this analysis on each of the primary and secondary objectives, if possible.*

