Risks: Exercise testing is a common procedure with minimal risks, but the test is monitored by a physician and will be stopped if problems occur. These include fainting, dizziness, chest pain, irregular heartbeats, or a heart attack, although the latter is extremely rare. The risks of this test are roughly 1 death in every 10,000 tests performed and serious adverse effects such as a heart attack or serious irregular heart beat (arrhythmias) requiring hospitalization occur in less than 1 in 1,000 tests. Blood pressure, heart rate and rhythm and breathing are closely and constantly monitored by a physician and exercise technician trained in CPR, exercise testing and emergency treatment of cardiac arrhythmias. This team has a specific, well-practiced protocol that includes contacting emergency services and providing interim medical support if needed.

- The participant may feel uncomfortable answering some of the questions. We will work with them to minimize this discomfort and no one has to answer any question that they do not wish to answer.
- There is a risk that participants will express suicidal thoughts or actions as we will be using the Beck Depression Inventory which queries suicidality. A suicidality protocol (attached) will be used in the case of a participant endorsing a suicidality item.
- There is a risk that confidential information might accidentally be disclosed. Professional standards for protecting confidential information will be used to minimize this risk.

Benefits: It is likely that those who complete CR will be healthier and have a higher quality of life than those who do not. However, just being in this study does not guarantee benefits.

This study will benefit society as a whole, however. Low-income patients are not recovering from cardiac events as well as higher-income patients. If we can find an effective way to engage them in appropriate post-cardiac care they will have better recovery and a higher quality of life. Improving outcomes in this vulnerable population could help narrow the gap in health outcomes between high and low income patients.

Therapeutic Alternatives: List the therapeutic alternatives that are reasonably available that may be of benefit to the potential subject and include in the consent form as well.

Not Applicable

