Cardiac-related symptoms will be rated at baseline and monitored during each participant contact (in person and by telephone) using scales that are operationally-defined, have good-to-excellent inter-rater reliability and are widely used in clinical and research settings. In addition, participants will be asked about their general health, symptoms and adverse events weekly during the study. Any clinically-significant symptom exacerbations noted during the study (i.e., changes in severity of existing symptoms, presentation of new symptoms) will trigger review and contact with the participant by the Medical Director [name]. Any serious adverse event and any unexpected and apparently related adverse event will trigger immediate review and contact with the participant by Medical Director [name] and will be reported by the PIs to the IRBs. Participants will be given study contact cards so that they can inform us of events that occur in between study visits. Monitoring by the PI is conducted on an ongoing basis and monitoring by the IRB is conducted at the continuing reviews as scheduled by the IRB and upon receiving reports of adverse events from the PIs.

Charge of DSMB. The DSMB will be charged with monitoring and evaluating two aspects of the clinical trial. These include: a) monitoring study progress; i.e., screening, recruitment, and retention data, to assure that the study can be completed in the time proposed, and b) reviewing safety data, especially serious adverse events (SAEs). SAEs, study or non-study related, will be reported to the DSMB, as well as to NIH, by the PI within 72 hours of the PI learning of the event. The DSMB will review all adverse events.

DSMB Members: Our DSMB will consist of four individuals. The DSMB will include members with experience in cardiac rehabilitation, lower-SES patients, conduct of clinical trials, and data analysis. It will include at least one physician and one researcher. The chair will have served on prior DSMBs.

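### Under contact restrictions the Beck Depression Inventory may be returned by mail, which delays the trigger for the suicidality protocol until the form is received and read

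*Combined protocol and SAP*

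**What the plan says.** Four parts of the protocol bear on this point.

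- **Questionnaire list (Procedures).** The BDI comes first, with a note on its content: "Beck Depression Inventory. Note: the BDI includes a question about suicidal thoughts". The action follows: "If a subject endorses this item research staff will follow the attached suicidality protocol". On timing: "Questionnaires will be administered at intake, after 4 months, and at one year". On setting: "All questionnaires will be administered in a private setting at the Cardiac Rehabilitation Facility".
- **Data Collection: Questionnaire Administration Amidst Contact Restrictions.** As far as practicable, "paper questionnaires will be completed remotely, either by mail (completed and returned by the study participant) or with the researcher over the phone". The section then names the measures that are dropped when staff cannot meet participants face to face; these "will not be collected: IQ test (WASI), Stop Signal Task (SST), Delay Discounting Task (DD), Trail Making Task (TMT), Digit Span Task". The BDI is not among them.
- **Risks/Benefits.** Expression of suicidal thoughts or actions is listed as a risk, with this response: "A suicidality protocol (attached) will be used in the case of a participant endorsing a suicidality item". The response is the same whatever the mode of completion.
- **Data Safety and Monitoring, Frequency of Monitoring.** Separately from the questionnaires, "participants will be asked about their general health, symptoms and adverse events weekly during the study".

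**The concern.** The suicidality protocol starts from an answer on a questionnaire, so it can start only once someone on the study team knows that answer. Over the telephone the researcher hears it as it is given. By mail, the participant may endorse the item at home and nobody on the study team knows until the envelope has arrived and the form has been read.

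The mail route is a permitted mode, so this delay would occur with staff following the plan as written. It would occur while participants may be isolated and staff have no face-to-face view of them. What is at stake is how promptly the study responds to a risk that the protocol itself identifies.

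**Working it through.** The documents state no figure on this point, so there is none to reproduce. The check is a reading of the sections against each other.

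1. **Is the BDI still collected under restrictions?** Yes, by inference. It is on the questionnaire list immediately before the contact-restriction section, and it is absent from the assessments that section drops (WASI, Stop Signal, Delay Discounting, Trail Making, Digit Span). The text does not say outright that the BDI is a paper form; that follows from its place in the list.
2. **May it be mailed?** Yes. The sentence offers mail or telephone for paper questionnaires and assigns no instrument to either route.
3. **What starts the response?** Endorsement of the BDI item, acted on by research staff (questionnaire list and Risks/Benefits). Neither place gives a time limit or a step specific to mailed forms.
4. **When is the endorsement known?** For a mailed form:

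   delay = time the participant holds the form + postal transit + time until it is opened and read.

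   The documents give none of the three terms, so the delay has no computable value. By telephone with the researcher, all three terms disappear.
5. **What is the in-person comparator?** The plan gives the setting (private, at the facility) but does not say that the BDI is read before the participant leaves. Same-day reading on site is plausible, but it is an inference. The firm comparison is therefore mail against telephone.
6. **How many administrations could be involved?** There are three scheduled occasions per participant, so the planned total is 209 × 3 = 627. This is a ceiling. It would be reached only if everyone were retained, restricted at all three time points and always mailed. The documents do not allow the actual number to be estimated, and they give no endorsement rate.
7. **Does other contact fill the gap?** The weekly enquiry covers health, symptoms and adverse events; it does not name suicidality or involve reading the BDI. When clinics stop in-person visits, cardiac rehabilitation (CR) includes a weekly telemedicine call, but this is a rehabilitation session within a programme of about 4 months and is not described as covering the item. Either contact might bring distress to light. Neither changes when a mailed answer is seen.

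**The case against.** The strongest objection is that the suicidality protocol is an attachment and was not available for review. It could already require the BDI to be done by telephone, set a time for reading returned forms, or say what a mailed pack must contain. This stands. It limits the point to the visible text and is the main reason for moderate confidence.

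Other objections have weight:

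- **Other contact exists.** Besides the weekly enquiries, clinically significant symptom changes lead to review and contact by the medical director, and participants hold contact cards. The two case-management arms have a case manager on the telephone Monday to Saturday. Current untreated Axis 1 disorder is excluded at entry. A reader might infer that the suicidality protocol is the only safeguard; the documents do not support that. Still, none of these measures is described as detecting an endorsed BDI item.
- **A returned form still triggers the response.** A reader might infer that the safeguard stops working by mail. It does not: it acts later. A form that never comes back is a missing assessment, as a missed visit would be, and should not be counted as an unlimited delay.
- **There is no contradiction in the text.** The contact-restriction section is an explicit exception to on-site administration, and staff may already choose the telephone. That is correct, but it leaves the slower route open for the one listed questionnaire that the plan links to a safety response.
- **Telephone has drawbacks.** A call at home may not be private, and participants may disclose less to an interviewer than on paper. Both are reasonable cautions, and the fix has to take account of them.
- **A lighter remedy exists.** The plan could state when returned BDIs are read. That would limit only the last term of the delay, leaving the holding time and the post.

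**Conclusion.** The point holds for the text available. Under contact restrictions the plan permits a mailed BDI, and for a mailed BDI the trigger for the suicidality protocol waits until the form is received and read. No visible passage limits that wait or reserves the BDI for telephone.

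The size cannot be expressed as a number of days or of participants; any such figure would be an outside assumption. The point rests on two assumptions: that the BDI is among the paper questionnaires, and that the unseen attachment does not already deal with mailed forms. If it does, a cross-reference in the contact-restriction section would be enough.

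A reader might extend the point to the PHQ-2, which is also named among the socio-cognitive measures. The documents link the suicidality item only to the BDI, so there is no basis here for including it.

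This is a participant-safety matter that should be corrected. It has no bearing on the primary outcome, sample size or power. Confidence is moderate.

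**What to change.** In the section on questionnaire administration under contact restrictions, add a sentence that exempts the BDI from the mail option. When it cannot be given in person, it is completed with the researcher by telephone, after confirming that the participant can speak privately, and the mode is recorded. The other questionnaires can keep both routes.

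Then reconcile the questionnaire list, the contact-restriction section and Risks/Benefits with the attached suicidality protocol, so that all four agree on how an endorsed item is detected when the BDI is completed remotely. The content of the suicidality protocol is not altered by this change.

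The cost is one sentence and a few minutes of researcher time per remote assessment. The statistical downside is a possible mode effect on a secondary measure: BDI scores obtained by interview may differ from those obtained on paper, and disclosure of the item itself may be lower. The existing text already allows a mix of on-site, mailed and telephone completion, so mode should be recorded in any case and its distribution by condition and time point described alongside the 4- and 12-month socio-cognitive results.
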